### 5.2 Inclusion Criteria

A subject must meet the following criteria to be eligible for the study:

1. Willing and able to read, understand and sign an informed consent form;
2. Male or female  $\geq$  18 years of age;
3. Documented diagnosis of pemphigus vulgaris or foliaceus based on all 3 of the following criteria:
  - a. Documented clinical history consistent with pemphigus vulgaris or foliaceus (clinical presentation defined as mucosal and/ or skin lesions);
  - b. Presence of Anti-Dsg 1 or 3 antibodies above the upper limit of normal;
  - c. History of at least one positive tissue based test (biopsy, DIF)
4. Active disease: Lesions lasting  $>$  2 weeks, and 3 active lesions in skin or mucosa or 2 active lesions with at least one being a skin lesion  $>$  1 cm diameter:
  - a. If treated with rituximab or other anti-CD20 antibodies, last dose  $>$  12 months prior to screening;
  - b. If being treated with other immunosuppressants (i.e., azathioprine, mycophenolate mofetil or cyclosporine), must be on stable dose ( $<$  10% change in dose) for 6 weeks prior to screening;
  - c. If being treated with corticosteroids, must be  $\leq$  1mg/kg/day and stable ( $<$  10% change in dose) for 2 weeks prior to screening;

- d. Allowed topical therapies for pemphigus lesions upon entering the study include petroleum jelly or Aquaphor® for the skin or chlorhexidine for the mouth
5. Body mass index (BMI) 18.5 – 35.0 kg/m^2;
6. Has a negative urine pregnancy test (for women of childbearing potential) documented prior to the first dose of study drug;
7. Females of childbearing potential must agree to be abstinent or else use any two of the following medically acceptable forms of contraception (<1% per year failure rate) from the Screening Period through 60 days after the final study dose: oral contraceptive, condom with or without spermicidal jelly, diaphragm or cervical cap with spermicidal jelly, or intra-uterine device (IUD). A female whose male partner has had a vasectomy must agree to use one additional form of medically acceptable contraception.
8. Females of non-childbearing potential, defined as surgically sterile (status post hysterectomy, bilateral oophorectomy, or bilateral tubal ligation) or post-menopausal for at least 12 months do not require contraception during the study.
9. Males with female partners of childbearing potential, including males who are surgically sterile (post vasectomy), must agree to be abstinent or else use a medically acceptable form of contraception from the screening period through 60 days after the final study dose.

### **5.3 Exclusion Criteria**

A subject who meets any of the following criteria is ineligible for the study:

1. Unable or unwilling to comply with the protocol;
2. Active non-hematologic malignancy or history of non-hematologic malignancy in the 3 years prior to screening (exclusive of non-melanoma skin cancer and cervical cancer in situ);
3. Positive for HIV or hepatitis C antibody;
4. Positive for hepatitis B surface antigen;
5. Active infection or history of recurrent infections;
6. IVIG treatment within 60 days of screening;

7. Received any cytotoxic (other than azathioprine) or mAb therapy in the 3 months prior to screening;
8. Any exposure to an investigational drug or device within 30 days prior to screening;
9. Plasmapheresis or immunoadsorption within 60 days of screening
10. Cellular therapy at any time prior to screening
11. Use of any immunosuppressive drugs apart from corticosteroids, azathioprine, mycophenolate mofetil, or cyclosporine within 3 months of screening;
12. Serum total IgG < 600 mg/dL;
13. Subject has any current medical condition that, in the opinion of the Investigator, may compromise their safety or compliance, preclude successful conduct of the study, or interfere with interpretation of the results (e.g., a significant pre-existing illness or other major comorbidity that the Investigator considers may confound the interpretation of the study results);
14. Any vaccination within 2 weeks of screening

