## LIST OF ABBREVIATIONS

ADA	Anti-drug antibodies
AE	Adverse event
AECA	Anti-epithelial cell antibody
ALT	Alanine aminotransferase
ANA	Antinuclear antibody
AST	Aspartate aminotransferase
ATC	Anatomical therapeutic chemical
AUC 0-24	Area under the plasma concentration-time curve from pre-dose (time 0) to 24 hours post-dose
AUC 0-∞	Area under the plasma concentration-time curve from pre-dose (time 0) to infinity
BLQ	Below the limit of quantification
BMI	Body mass index
BUN	Blood urea nitrogen
CAR-T	Chimeric antigen receptor and T-cell
CFR	Code of Federal Regulations
C3	Complement component 3
CBC	Complete blood count
CIC	Circulating immune complexes
CIDP	Chronic inflammatory demyelinating polyneuropathy
C max	Maximum plasma concentration determined directly from the concentration-time profile
CRO	Contract research organization
CV	Coefficient of variation
CVID	Common variable immune deficiency
DEC	Dose escalation committee
D5W	Dextrose 5% in Water
DIF	Direct immunofluorescence
DNA	Deoxyribonucleic acid
ECG	Electrocardiogram
eCRF	Electronic case report form
ESR	Erythrocyte sedimentation rate
FcGR2a	Fc Gamma R2a receptor
FcRn	Neonatal Fc receptor
FDA	Food and Drug Administration
GCP	Good Clinical Practice
GI	Gastrointestinal
HBV	Hepatitis B virus
HCV	Hepatitis C virus
HIPAA	Health Insurance Portability and Accountability Act
HIV	Human immunodeficiency virus
IB	Investigator's brochure
IC	Immune complex

---

ICF	Informed consent form
ICH	International Conference on Harmonization
IgA	Immunoglobulin A
IgG	Immunoglobulin G
IgG1-4	Immunoglobulin G1-G4
IgM	Immunoglobulin M
IL-12	Interleukin 12
IND	Investigational new drug
IRB	Institutional review board
ITT	Intent-to-treat
IUD	Intrauterine devices
IV	Intravenous
IVIG	Intravenous immunoglobulin
MedDRA	Medical Dictionary for Regulatory Activities
NHL	Non-Hodgkin lymphoma
PD	Pharmacodynamics
PE	Physical examination
PK	Pharmacokinetic
RBC	Red blood cells
RNAseq	RNA sequencing
QTcF	Corrected QT interval using Fridericia's formula
SAE	Serious adverse event
SAP	Statistical analysis plan
SAS	Statistical Analysis System
SD	Standard deviation
SNP	Single nucleotide polymorphism
SOC	System Organ Class
SOP	Standard operating procedures
SYNT001	A humanized, affinity matured IgG4-kappa monoclonal antibody
$t_{1/2}$	Half-life
TEAE	Treatment-emergent adverse event
$T_{max}$	Observed time to reach peak plasma concentration
TNF	Tumor necrosis factor
ULN	Upper limit of normal
UNS	Unscheduled

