### 9.6.2 Potential Immune Effects

An antibody blocking FcRn is anticipated to have several effects. These include acceleration of catabolism of IgG, but not other immunoglobulin isotypes such as IgA and IgM, leading to dose-dependent decreases in circulating IgG levels by up to an estimated 50% from the baseline levels after a single dose and further decreases after multiple doses up to a 70% to 80% reduction. Based on studies in humans, it is expected that with a single dose, the nadir of this effect will occur approximately 5 days after dosing. The time course of recovery of IgG following dosing in the Phase 1a study suggests that a return to within normal limits occurs within 4 weeks after a single dose and within 4 weeks after multiple doses as shown in NHPs.

Given the normal adult range of IgG of 700 to 1600 mg/dL (in some references), with a mean of 1150 mg/dL, a 50% decrease in the mean would be to 575 mg/dL and a 50% decrease from the low end of the normal range of 700 mg/dL would be to 350 mg/dL. An 80% decrease from baseline after multiple doses would result in IgG levels of 230 mg/dL and 140 mg/dL, respectively. While these levels are in the range found in patients with primary humoral immunodeficiency [[Ameratunga 2013](#)], the levels will be transient. Study subjects will be monitored clinically for any infection. Further, commercial IVIG can be given to reverse the low IgG levels in case of a bacterial infection occurring while their IgG levels are decreased.

An antibody blocking FcRn is expected to also down modulate innate and adaptive immunity and the catabolism of IgG-containing immune complexes (IC). Specifically, it is expected that anti-FcRn will promote the clearance of IgG-containing ICs and the effects of these IC on stimulating innate immune cell production of inflammatory cytokines (e.g., IL-12, interferon- $\gamma$ , and tumor necrosis factor [TNF]) and inhibit the processing and presentation of antigens contained within IC and thus the antigen-specific activation of CD4+ and CD8+ T-cells. Therefore, subjects with pre-existing conditions that are dependent upon IgG antibodies, such as chronic infections (e.g., HIV, HBV or HCV), will be excluded from this study, as will subjects with active infection in general.

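### Exclusion 2 sets a fixed bar only for non-hematologic cancer; blood cancers are left to investigator discretion or incidental criteria, and the protocol gives no reason

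*Protocol*

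**What the plan says.** Protocol Section 5.3, item 2, excludes "Active non-hematologic malignancy or history of non-hematologic malignancy in the 3 years prior to screening", with exceptions for non-melanoma skin cancer and in-situ cervical cancer. The synopsis has the same wording, as does the second copy of the protocol text in the same file. The qualifier stands twice in the item, once for active disease and once for history.

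Item 13 is a general discretionary exclusion: "Subject has any current medical condition that, in the opinion of the Investigator, may compromise their safety or compliance". It extends to conditions that may "interfere with interpretation of the results (e.g., a significant pre-existing illness or other major comorbidity".

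Other criteria touch blood cancers only through treatment or laboratory values. Item 7 reads "Received any cytotoxic (other than azathioprine) or mAb therapy in the 3 months prior to screening", item 10 "Cellular therapy at any time prior to screening" and item 12 "Serum total IgG < 600 mg/dL".

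Section 9.6.2 explains the eligibility thinking on immune risk: "subjects with pre-existing conditions that are dependent upon IgG antibodies, such as chronic infections (e.g., HIV, HBV or HCV), will be excluded". It expects IgG to fall by up to about half after one dose and by up to 70 to 80% after several.

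**The concern.** The fixed rule and the biology of the drug point in different directions. A solid tumor two years in remission is a firm exclusion at every site. An untreated cancer of the B-cell or plasma-cell line, the cells that make IgG, is not, although it bears more directly on an IgG-lowering antibody.

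Three things are at stake.

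- **Safety, the primary objective.** A subject whose antibody production is already impaired could be taken to very low IgG.
- **Interpretation.** Total IgG is the pharmacodynamic effect used to choose the doses (Section 2.2) and stands first among the pharmacodynamic outcomes (Section 4.2). B-cell phenotyping is an exploratory outcome. A B-lineage malignancy could affect both.
- **Escalation.** Infections or cytopenias caused by the malignancy might, if judged drug-related, count toward the Grade 3 rule in Section 8.4.1.

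**Working it through.** The plan states no statistical figure on this point, so the check is mainly a reading of all 9 inclusion and 14 exclusion criteria against typical cases.

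**Criteria that name blood cancer:** 0 of 14 exclusions and 0 of 9 inclusions.

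**Who is stopped, and by what:**

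- Solid tumor, in remission for two years: fixed exclusion under item 2.
- Blood cancer given cytotoxic therapy other than azathioprine, or an antibody, within 3 months: fixed exclusion under item 7. Item 11 adds other immunosuppressants over the same 3 months.
- Blood cancer given an anti-CD20 antibody within 12 months: stopped by inclusion 4a, which does not depend on why the antibody was given.
- Blood cancer ever treated with cellular therapy: fixed exclusion under item 10.
- Blood cancer with active or recurrent infections: fixed exclusion under item 5.
- Blood cancer with total IgG below 600 mg/dL: fixed exclusion under item 12.
- Active, untreated blood cancer with total IgG of 600 mg/dL or more and no active or recurrent infections: no fixed exclusion. Only item 13 applies, at the investigator's discretion.
- Blood cancer in remission but within 3 years, with no anti-CD20 in the last 12 months, no other barred therapy in the last 3 months, and no cellular therapy: no fixed exclusion. Item 13 may not apply, because it addresses a current condition.

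The last two lines are the gap.

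**What item 12 protects.** The figures in Section 9.6.2 reproduce:

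- 1150 × (1 − 0.80) = 230 mg/dL
- 700 × (1 − 0.80) = 140 mg/dL

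The section itself places these levels in the range of primary humoral immunodeficiency, while noting that they would be transient. At the item 12 floor the same reasoning gives:

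- 70% fall: 600 × 0.30 = 180 mg/dL
- 80% fall: 600 × 0.20 = 120 mg/dL

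Item 12 is a lower limit on total IgG with no upper limit. A monoclonal IgG that is counted in the total could keep a subject above 600 mg/dL while functional antibody is low.

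**Weight of one subject.** One of 8 is 1/8 = 12.5% of a cohort summary. Section 8.4.1 halts the cohort and escalation at 2 subjects with clinically significant, drug-related Grade 3 events, so one such subject can supply at most one of the two.

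**The case against.** The strongest reply is exclusion 13. It names the two harms at issue, compromised safety and compromised interpretation, and meeting any one criterion makes a subject ineligible. A reader might infer from item 2 that a subject with active lymphoma, leukemia or myeloma is simply eligible, or that nothing else closes the gap. The documents do not support that. An active case can be excluded under item 13, and inclusion 4a and exclusions 5, 7, 10, 11 and 12 catch further cases. The remaining group is narrow.

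Other limits also stand.

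- The Grade 3 count requires relatedness, and Section 11.3.5 lists a pre-existing condition as grounds for calling an event unrelated. Progression of the cancer would not automatically enter the count. On the other hand, the same section lists a positive temporal relationship, on its own, as consistent with relatedness.
- The IgG endpoint is change from baseline within a subject. Nothing in the documents shows how far an indolent blood cancer would alter that change over 56 days.
- The 12.5% figure would apply to any subject with any comorbidity.
- Section 9.6.2 illustrates its principle with chronic infections and does not mention malignancy, so it does not contradict item 2.
- The abbreviation list contains "Non-Hodgkin lymphoma" and CAR-T, which the body text does not use. A reader might infer that item 2 was carried over from another protocol. That is only suggestive and cannot be checked here.

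What the reply does not answer is why a discretionary bar should suffice for blood cancers at approximately 10 sites when every other cancer has a fixed one. Limiting item 2 expressly to non-hematologic disease may even lead an investigator to read blood cancer as deliberately allowed. It also leaves past blood cancer within 3 years without a clear rule.

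**Conclusion.** The point holds as an unexplained and poorly fitting eligibility rule, not as an outright admission of active blood cancer. Item 2 omits hematologic malignancy in every copy. An active case depends on investigator judgement or on incidental criteria, and a case in remission within 3 years may meet none.

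The likelihood is low and the documents give no prevalence, so no expected number of subjects can be calculated. The consequence per subject is one eighth of a cohort and at most one of the two events that stop it. The conclusion rests on two assumptions: that item 13 is applied as worded, to current conditions and by opinion, and that sites treat item 2 as the governing rule on cancer. The change is worth making because it favors both subject safety and the interpretability of IgG, at almost no cost.

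**What to change.** Reconcile item 2 with items 12 and 13 and with Section 9.6.2. The simplest way is to delete the qualifier non-hematologic both times it occurs in item 2, in Section 5.3 and in the synopsis, so that the item covers any malignancy, active or within 3 years, with the existing exceptions unchanged. If the omission is intended, the protocol should say why hematologic malignancy is admitted and how that fits with the expected fall in IgG.

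The cost is a wording change in an amendment. No new test is needed, because Section 6.2 already collects current and past disease. The downside is a very small loss of eligible subjects.

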## **6 STUDY PROCEDURES**

### **6.1 Informed Consent**

All subjects must take part in the informed consent process. Adequate time must be allowed for the subject to ask questions and make a voluntary decision. No protocol-specific procedures, including screening procedures, are to be performed until the subject has signed and dated an IRB-approved ICF. Subjects may withdraw consent at any time. Participation in the study may be terminated at any time without the subject's consent as determined by the Investigator.

### **6.2 Demographics and Medical History**

Demographics (age, gender, race and ethnicity) and medical history will be obtained from the subject and recorded on the source document and eCRF. Medical history will capture the subject's current medical history (current disease processes), past medical status (past disease processes), history of surgery and concomitant treatments.

### **6.3 Physical Examination**

A complete physical examination will be performed as outlined in [Table 1](#). The complete PE will include measurements of weight (in kg) and height (in cm; height to be measured only at screening visit) and a review of the following body systems:

- General appearance
- Head, eyes, ears, nose, and throat
- Neck
- Respiratory
- Cardiovascular
- Abdomen
- Neurologic
- Extremities
- Dermatologic
- Lymphatic

Any abnormal and clinically significant findings from the PE must be recorded in the appropriate eCRF. Findings at screening and Day 0 (pre-dose) will be recorded as medical history.

### **6.4 Pemphigus Disease Area Index (PDAI) Scoring**

Pemphigus severity and disease activity will be measured using the PDAI. See [Appendix B](#).

### **6.5 Vital Sign Measurements**

Vital sign measurements will be collected after the subject has been sitting for 5 minutes. Vital sign assessments will include measurements of sitting blood pressure (mm Hg), heart rate (beats

---

per minute), respiration rate (breaths per minute), oral temperature (Celsius). Abnormal results are to be repeated after 5 minutes of rest. Pulse oximetry (%) also is to be measured. See [Table 2](#) for timing window allowances with respect to measurement collection.

On Days 0, 7, 14, 21, and 28, vital sign measurements are to be obtained immediately prior to the infusion; 15, 30, and 45 minutes after the start of the infusion; at completion of the infusion; and 30 minutes, 1 hour and 2 hours following completion of the infusion. Details on the management of mild to moderate and severe infusion reactions can be found in [Figure 1](#) and [Figure 2](#). Abnormalities in vital sign measurements will be graded in severity per the NCI CTCAE scale Version 4.03.

Subjects should be seated quietly for at least 5 minutes in a chair with their backs supported, their feet flat on floor (legs uncrossed), and their arms bared on a hard surface, with the arm slightly abducted and bent, with palm up and the midpoint of upper arm at heart level. Correct cuff and bladder size should be utilized and the same cuff and arm should be used per subject throughout study.

#### **6.6 12-Lead Electrocardiogram (ECG)**

Digital 12-lead ECG measurements will be obtained at screening, on Days 0 and 28 at 5 minutes after the completion of the infusion and at the Day 56 (Follow-Up) Visit. Subjects who conduct their Day 12 visit at the investigative site, as opposed to an at-home nurse visit, will have an additional ECG performed. ECGs are to be performed with the subject in a supine position having rested in this position for at least 5 minutes before each reading. ECGs are to be performed in triplicate, each 1 to 2 minutes apart. See [Table 2](#) for timing window allowances with respect to performing ECG.

The following ECG parameters will be collected: PR interval, RR interval, QRS interval, and QT interval. The ECG findings will be evaluated by a qualified physician for the presence of abnormalities (qualitative assessment). The physician will assess each ECG as normal, abnormal/not clinically significant, or abnormal/clinically significant.

Normal QTcF is  $\leq 450$  msec.

Abnormalities in the ECG that appear following therapy or that result in clinical signs and symptoms are considered clinically significant for the purposes of this study and will be recorded on the AE eCRF.

## 6.7 Clinical Laboratory Measurements

Collection time for all safety, PD, and exploratory labs are outlined in [Table 1](#).

Laboratory testing (hematology, urinalysis, serum chemistry, virology, serology, pregnancy tests, PD samples, PK samples, and anti-drug antibody samples) will be performed using established methods by a central laboratory. Safety laboratory panels are defined as listed in Table 3. Blood and urine samples for hematology, serum chemistry, and urinalysis will be prepared using standard procedures. Results will be provided to the Investigator. Aliquots from the PK, biomarker and anti-drug antibody samples may be retained as back-up for additional testing as necessary. Subjects will be in a seated or supine position during blood collection. Full clinical safety lab draws will be collected at Screening and on Days 0, 7, 14, 21, 28, 33, 42 and 56. The total blood draw for each subject who completes the study at Day 56, will be approximately 308 mL. Please refer to the Laboratory Manual for more information.

**Table 3: Clinical Laboratory Panels**

Hematology	Serum Chemistry	Urinalysis

 
CBC with differential
 
Erythrocyte Sedimentation Rate (ESR)
 
	
 
Albumin
 
Alkaline phosphatase
 
ALT
 
AST
 
BUN
 
Calcium
 
Carbon dioxide
 
Chloride
 
Creatinine
 
Glucose
 
LDH
 
Phosphorus
 
Potassium
 
Sodium
 
Total and direct bilirubin
 
Total protein
 
Uric acid
 
C-Reactive Protein
 
	
 
Appearance
 
Color
 
pH
 
Specific gravity
 
Ketones
 
Protein
 
Glucose
 
Nitrite
 
Urobilinogen
 
Blood/hemoglobin
 
Leukocyte esterase
 
Bilirubin
 
Microscopic examination of sediment: only if the results of the urinalysis dipstick evaluation are positive for blood/hemoglobin
 

Virology		

 
Hepatitis C
 
Hepatitis B
 
		

- 
- HIV
  - VZV
  - Tetanus
- 

ALT = alanine aminotransferase; AST = aspartate aminotransferase; CBC = complete blood count; BUN = blood urea nitrogen; HIV = human immunodeficiency virus; LDH = lactate dehydrogenase; VZV = varicella-zoster virus

Abnormalities in clinical laboratory tests that are considered clinically significant are to be recorded on the AE electronic case report form (eCRF) page. Laboratory results will be graded using the NCI CTCAE, Version 4.03. If laboratory values constitute part of an event that meets criteria defining it as serious, the event (and associated laboratory values) must be reported as an SAE (see [Section 11.3.1](#)).

#### **6.7.1 Pregnancy Testing**

Pregnancy testing will be performed for women of childbearing potential at screening and prior to first dose of SYNT001 on Day 0 and Day 56 (urine or serum test is acceptable however, positive urine tests must be confirmed with serum testing.)

#### **6.7.2 Virology**

Testing for HCV antibody, hepatitis B surface antigen, and HIV antibody will be performed at screening.

